### 4.5.1. Extent of Exposure

The exposure data will be reported for Cohort 1 and Cohort 2.

For each treatment and period, dose administration and exposure data for all participants will be generated in the listing for Safety analysis set.

### 4.5.2. Adverse Events

The applicable definition of an AE and SAE are in the study protocol Sections 8.4 and 10.3.

All reported AEs will be coded using the standard GSK dictionary, (MedDRA  $\geq$  26.1 version).

An AE is considered study treatment emergent (on-treatment) if the AE onset date is on or after study treatment start date and on or before study treatment stop date plus 1 day (inclusive) follow-up or worsens (change in AE severity from lower severity to higher severity category) relative to the pre-study treatment state.

AEs occurring following dosing in a specific period but before dosing in the next period will be attributed to that specific period. If the time is missing for an AE on a dosing day then the AE will be attributed to the treatment given on that day.

Overview of AEs:

The following points will be presented in a summary table for overview of AEs in overall (on and post-treatment) and on-treatment period.

- Total number of AEs reported with the number of participants who experienced at least one AE
- AE by maximum severity intensity
- Drug-related AE and SAE, non-fatal SAE, drug-related non-fatal SAE
- SAE leading to death
- AE leading to discontinuation of study treatment and AE leading to withdrawal from study

AEs and SAEs by SOC and PT:

The below summaries (counts and percentages) will be produced for AEs and SAEs by system organ classes (SOC) and (PT) for overall (on- and post-treatment) and on-treatment period.

- Summary of AEs by SOC and PT
- Summary of SAEs by SOC and PT
- Summary of SAEs by SOC and PT with number of subjects and occurrences

Common AEs:

The following summaries (counts and percentages) will be displayed for common ( $\geq 10\%$  incidence, before rounding) AEs for overall (on- and post-treatment) and on-treatment period.

- Summary of common ( $\geq 10\%$ ) AEs by PTs
- Summary of common ( $\geq 10\%$ ) Non-SAEs by SOCs and PTs with number of subjects and occurrences

AEs and SAEs related to study treatment:

Relationship to study treatment, as indicated by the investigator, is classified as “not related” or “related”. AEs with a missing relationship to study treatment will be recorded as “related” to study treatment. If a participant reports the same AE more than once within an SOCs/PTs, the AE with the worst-case relationship to study treatment will be used in the corresponding relationship summaries.

The following summaries (counts and percentages) will be presented for drug-related AEs and SAEs for on-treatment period.

- Summary of drug-related AEs by overall frequency
- Summary of drug-related SAEs by overall frequency

Summary of serious fatal and non-fatal drug-related AEs will be generated by overall frequency. Summary of non-serious drug-related AEs by overall frequency will also be created.

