- j. **MDI training:** Participants will be trained using a placebo HFA-134a propellant via an MDI on Day-1 and prior to dosing on each dosing day (Day 1, 4, 7 and 10). On dosing days, participants should review the instructions use the placebo MDI. The investigator or delegate are to observe the participant performing a single puff using the placebo MDI and provide feedback as necessary until proper technique is observed before conducting the full dose using the investigational inhaler. Additional training using the placebo MDI (e.g., on Day 3) may be performed at the discretion of the site.
- k. **Administration of study intervention:** 8 inhalations of 100 µg (800 µg total) of study intervention or 2 inhalations of 100 µg (200 µg total) of study intervention, with the inhalations administered at 20-second intervals.
- l. **PK blood sampling:** on each dosing day (Day 1, 4, 7 and 10) PK blood samples will be taken at predose, at 3, 5, 10, 15-, 20-, 30-, and 45-minutes postdose; and at 1, 1.5, 2, 3, 4, 5, 6, 8, 10-, 12-, 16- and 24-hours postdose for plasma salbutamol determination. PK collection will be from the start of study intervention (first inhalation).
- m. **AE and SAE review:** AEs will be collected from the start of study intervention until final follow-up telephone call. SAEs will be collected from the signing of the ICF until final follow-up telephone call.

Table 2 Timing of Assessments

Assessment	Timing of Dosing
Study intervention administration	Dosing for each participant will be around the same time (± 1 hour) at each intervention period day. All postdose timepoints will be from the start of each study intervention i.e., the first inhalation.
PK blood sampling	Predose samples will be obtained between waking up and dosing. Postdose samples up to 30 minutes will be obtained with a time window of ± 1 minute. Thereafter, postdose samples will be obtained with time margins of $\pm 5\%$ of the time that has passed since (last) dosing.
PD blood sampling	For PD blood samples, predose samples will be obtained between waking up and dosing. Postdose samples up to 30 minutes will be obtained with a time window of ± 2 minutes. Thereafter, postdose samples will be obtained with time margins of $\pm 5\%$ of the time that has passed since (last) dosing.

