8.4.1. Time period and frequency for collecting AE, SAE, and other safety information

All SAEs will be collected from the signing of the ICF until final follow-up telephone call at the time points specified in the SoA.

SAEs assessed as related to study participation (e.g., study intervention, protocol-mandated procedures, invasive tests, or change in existing therapy) or related to a GSK product (non-IMP) will be recorded from the time a participant consents to participate in the study.

All AEs will be collected from the start of study intervention until final follow-up telephone call at the timepoints specified in the SoA.

Medical occurrences that begin before the start of study intervention but after obtaining informed consent will be recorded as medical history/current medical conditions, not as AEs.

All SAEs will be recorded and reported to the sponsor or designee immediately and under no circumstance should this exceed 24 hours, as indicated in Section 10.3. The investigator will submit any updated SAE data to the sponsor within 24 hours of it being available.

A poststudy AE/SAE is defined as any event that occurs outside of the AE/SAE reporting period defined in Section 8.4.3.

Investigators are not obligated to actively seek information on AEs or SAEs after conclusion of the study participation. However, if the investigator learns of any SAE, including a death, after a participant has been discharged from the study, the investigator must record it in the medical records. If the investigator considers the event to be reasonably related to the study intervention or study participation, the investigator must promptly notify the sponsor.

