10.3.1. Definition of AE

AE definition

 • An AE is any untoward medical occurrence in a clinical study participant, temporally associated with the use of a study intervention, whether or not considered related to the study intervention. • NOTE: An AE can therefore be any unfavorable and unintended sign (including an abnormal laboratory finding), symptom, or disease (new or exacerbated) temporally associated with the use of a study intervention.
Events Meeting the AE Definition

 • Any abnormal laboratory test results (hematology, clinical chemistry, or urinalysis) or other safety assessments (e.g., ECG, radiological scans, vital signs measurements), including those that worsen from baseline, considered clinically significant in the medical and scientific judgment of the investigator (i.e., not related to progression of underlying disease). • Exacerbation of a chronic or intermittent pre-existing condition including either an increase in frequency and/or intensity of the condition. • New condition detected or diagnosed after study intervention administration even though it may have been present before the start of the study. • Signs, symptoms, or the clinical sequelae of a suspected intervention- intervention interaction. • Signs, symptoms, or the clinical sequelae of a suspected overdose of either study intervention or a concomitant medication. Overdose per se will not be reported as an AE/SAE unless it is an intentional overdose taken with possible suicidal/self-harming intent. Such overdoses should be reported regardless of sequelae. • Events that occur as a result of protocol-mandated procedures (i.e., invasive procedures, modification of participant's previous therapeutic regimen).
Events NOT Meeting the AE Definition

 • Any clinically significant abnormal laboratory findings or other abnormal safety assessments that are associated with the underlying disease, unless judged by the investigator to be more severe than expected for the participant's condition. • Medical or surgical procedure (e.g., endoscopy, appendectomy): the condition that leads to the procedure is the AE. • Situations in which an untoward medical occurrence did not occur (social and/or convenience admission to a hospital, admission for routine examination.).

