#### **Treatment Period 1 (Day1):**

Treatment Period 1 dose start time <= Treatment Period 1 < Treatment Period 2 dose start time

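### Adverse events that start after the HFA-134a placebo training puff on Days 4, 7 and 10 but before that day's dose are tabulated under the previous period's product, inflating both product columns about equally

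*SAP*

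**What the plan says.** Footnote j of the schedule of activities (Protocol 1.3) sets the training: "Participants will be trained using a placebo HFA-134a propellant via an MDI on Day-1 and prior to dosing on each dosing day". On dosing days this involves a real inhalation: staff are to "observe the participant performing a single puff using the placebo MDI and provide feedback as necessary until proper technique is observed". HFA-134a is the propellant of the reference product.

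SAP 4.5.2 attributes adverse events to periods by time: "AEs occurring following dosing in a specific period but before dosing in the next period will be attributed to that specific period". The derivations in SAP 6.2.2 use the same cut, for example "Treatment Period 1 dose start time <= Treatment Period 1 < Treatment Period 2 dose start time", and Periods 2 and 3 are built the same way. For untimed events SAP 4.5.2 adds: "If the time is missing for an AE on a dosing day then the AE will be attributed to the treatment given on that day". SAP 4.5 has safety summarized by study treatment.

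Protocol Table 4 does not list the training placebo as a study intervention, and the schedule of activities keeps training and dosing in separate rows. No visible text in either document gives events after a training puff a category of their own.

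**The concern.** Take a participant in sequence TRRT who coughs after the Day 4 training puff and before the Day 4 dose. The last study product was HFA-152a, about three days earlier; the propellant just inhaled was HFA-134a. The SAP rule counts the cough under HFA-152a. If the onset time is missing, the event goes to the Day 4 product, which had not been given when the cough began.

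The protocol itself makes such reactions plausible. Section 6.5 says the placebo inhalers are used partly so that participants know the cold sensation of the propellant before dosing, and Section 3.1 lists coughing on dosing as an intercurrent event.

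At stake is the secondary safety objective, which describes tolerability for each product in a study of a propellant change. The affected displays are the all-AE, system organ class and preferred term, severity and common-AE tables. The pharmacokinetic analyses are untouched.

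**Working it through.** The plan gives no figure for this point, so there is none to reproduce. The check applies the stated rule to each scheduled session.

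**Inputs**
- Sequences TRRT and RTTR, 15 participants each per cohort (Protocol 4.1 and 9.5).
- Training before dosing on Days 4, 7 and 10 (Protocol 1.3, footnote j).
- Period boundary at dose start (SAP 4.5.2 and 6.2.2).
- Reaction rate per session: not in the documents; 1% to 5% is assumed for illustration.

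**Sessions per cohort after the first dose:** 30 × 3 = 90.

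**Product to which a timed pre-dose event is booked (sessions)**

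| Day | TRRT (15) | RTTR (15) | Under T | Under R |
|---|---|---|---|---|
| 4 | T | R | 15 | 15 |
| 7 | R | T | 15 | 15 |
| 10 | R | T | 15 | 15 |
| Total | | | 45 | 45 |

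The split is 15 to 15 on each day, so it stays balanced even if reactions become rarer as participants get used to the inhaler. With 14 completers per sequence it is 42 to 42.

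**Untimed events** go to that day's product. Day 4 is R in TRRT and T in RTTR, Day 7 is R and T, and Day 10 is T and R. The split is again 45 to 45. The previous and current products differ on Days 4 and 10, that is in 60 of the 90 sessions, so a missing time changes the column in two thirds of them.

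**Expected events per product per cohort**, if every reaction starts before the first actuation:
- at 1%: 45 × 0.01 = 0.45
- at 5%: 45 × 0.05 = 2.25

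**Expected participants with at least one such event under T:** 15 × r + 15 × [1 − (1 − r)²].
- at 1%: 0.15 + 0.30 = 0.45
- at 5%: 0.75 + 1.46 = 2.21, or about 7.4% of 30

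The common-AE threshold in SAP 4.5.2 is 10%, which is 3 participants out of 30. One or two such events could carry a preferred term over that line in either column.

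**Untimed events on Day 1.** SAP 4.5.2 gives an untimed adverse event on a dosing day to that day's treatment. SAP 6.2.2 treats an assessment with missing time on the first dose date as pre-treatment. The two rules give different answers for the same record.

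**The case against.** Booking events to the most recent study product is a simple, prespecified crossover convention, and the safety displays are descriptive with no between-product test. The investigator must weigh alternative causes and timing for every event (Protocol 10.3.4.3). A cough minutes after a placebo puff and three days after a dose can be judged not related, which keeps it out of the drug-related summaries, and listings by treatment and period will show it. This stands, with two limits: a missing judgement is counted as related (SAP 4.5.2), and the all-AE, severity and common-AE tables carry the event whatever the judgement.

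A reader might infer that the rule loads reference-propellant reactions onto the test product alone. The 45 to 45 split rules that out. Equal expected additions leave the absolute difference essentially unchanged; only a ratio is drawn toward 1.

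A reader might also infer that reactions to the Day -1 and Day 1 training are lost, or that Protocol 8.4.1 flatly contradicts 10.3.1. Section 8.4.1 says: "Medical occurrences that begin before the start of study intervention but after obtaining informed consent will be recorded as medical history/current medical conditions". Non-serious events are thus recorded, though not as adverse events, and serious ones are collected from consent. Section 10.3.1 does list "Events that occur as a result of protocol-mandated procedures", but under a definition tied in time to the use of a study intervention. Starting collection at the first dose is a coherent choice. Footnote j also specifies the observed puff for dosing days only, so a Day -1 inhalation is likely but not stated.

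Finally, part of the partial-date text (SAP 6.2.6) and the section on changes to protocol-defined analyses (SAP 4.8) are redacted, and the displays are detailed in programming specifications outside these documents. A related flag there cannot be excluded, but the rule for timed events is explicit in the visible text.

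**Conclusion.** The point holds as a misattribution in descriptive secondary tables. A timed event that starts after the training puff on Day 4, 7 or 10 and before that day's first actuation is shown under the previous product. That product is HFA-152a in 45 of 90 sessions per cohort and HFA-134a in the other 45. Both columns are inflated about equally, and some HFA-134a reactions appear under HFA-152a.

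The session counts follow from the design with full completion. The event counts, about 0.5 to 2.3 per product per cohort, rest on an assumed 1% to 5% reaction rate and on every reaction starting before dosing. The documents give neither the rate nor the gap between training and dosing. If only a fraction of reactions start in that gap, the number handled by the previous-period rule falls in proportion.

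The documents do not support a claim of bias against the test product, of unrecorded events, or of any effect on the pharmacokinetic results. The change is worth making because the attribution is plainly wrong for these events and cheap to correct.

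**What to change.** Add to SAP 4.5.2 that an adverse event on Day 4, 7 or 10 with onset from the start of that day's placebo training to the first actuation of study intervention is shown in a separate category, *training placebo (HFA-134a)/pre-dose*, and not under T or R. Record the training time alongside the adverse event onset time on those days. This would take the sessions booked to each product from 45 to 0 per cohort for timed pre-dose events.

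The cost is one extra column in the adverse event tables and one time field. The change does not reach every case: a reaction to the puff that starts after the first actuation still goes to that day's product, and an untimed event still follows the same-day rule.

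Separately, reconcile SAP 4.5.2 with SAP 6.2.2 on untimed Day 1 events so that one rule applies. Starting adverse event collection at the Day -1 training is optional and not needed for this fix. It would be a protocol amendment affecting the schedule of activities and its footnote m, Protocol 8.4.1 and the study period definitions in SAP 6.2.2.

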### AEs and SAEs by severity:

Adverse event severity is categorised as mild, moderate, severe. Adverse events starting after the first dose of study treatment with a missing severity will be classified as severe. If a participant reports an AE more than once within an SOCs/PTs, the AE with the worst-case (maximum) severity will be used in the corresponding severity summaries.

The following summaries (counts and percentages) will be produced for severity of AEs and SAEs by SOCs, PTs, and maximum severity in overall (on- and post-treatment) and on-treatment period.

- Summary of AEs by SOC and PT and maximum severity
- Summary of SAEs by SOC and PT and maximum severity

The below summaries (counts and percentages) for AEs and SAEs leading to permanent discontinuation of study treatment by SOCs and PTs will be generated in overall (on- and post-treatment) and on-treatment period.

- Summary of AEs leading to permanent discontinuation of study treatment or withdrawal from study by SOC and PT
- Summary of SAEs leading to permanent discontinuation of study treatment or withdrawal from study by SOC and PT

Adverse events analyses including the analysis of AEs and SAEs will be based on GSK Core Data Standards.

Separate listings will be produced of all AEs for each treatment and period in Safety analysis set. Summary of death will be summarized and participants profile for death will also be listed using Enrolled participants.

In summary tables, SOCs will be sorted in descending order of the total incidence then alphabetically, PTs will be sorted in descending order of the total incidence then alphabetically within the SOC.

For completely missing or partial missing AE start date or end date, imputation rules will be applied following Appendix 2 Section [6.2.6](#).

#### **4.5.2.1. Adverse Events of Special Interest**

No adverse events of special interest (AESI) are identified for the study therefore no statistical analysis will be performed for AESI.

#### **4.5.3. Additional Safety Assessments (if applicable)**

##### **4.5.3.1. Laboratory Data**

Laboratory evaluations including the analyses of chemistry laboratory tests, hematology laboratory tests and urinalysis will be as per below described [Table 6](#) (refer protocol Appendix 2, Section 10.2).

**Table 6 Parameters of laboratory tests assessments**

Laboratory Tests	Parameters	
Hematology	
 
• Platelet count
 
• Red blood cell (RBC) count
 
	
	RBC indices	
 
• Mean corpuscular volume (MCV)
 
• Mean corpuscular hemoglobin (MCH)
 
• %Reticulocytes
 

	Absolute WBC count with differential:	
 
• Neutrophils
 
• Lymphocytes
 
• Monocytes
 
• Eosinophils
 
• Basophils
 

	Hemoglobin	
	Hematocrit	
	
 
• Blood urea nitrogen (BUN)/Urea
 
• Potassium**
 
• Creatinine*
 
• Sodium
 
• Calcium
 
• Glucose fasting**
 
• Creatine phosphokinase(CPK)
 
	
	
 
• Aspartate aminotransferase (AST)/serum glutamic-oxaloacetic transaminase (SGOT)
 
• Alanine aminotransferase (ALT)/serum glutamic-pyruvic transaminase (SGPT)
 
• Alkaline phosphatase
 
• Total bilirubin
 
• Direct bilirubin
 
• Total protein
 
	
Routine urinalysis	
 
• Specific gravity
 
• pH, glucose, protein, blood, ketones, [bilirubin, urobilinogen, nitrite, leukocyte esterase] by dipstick
 
• Microscopic examination. Please note, this will only be performed if there is an abnormality in accordance with Clinical Laboratory standard procedures.
 
• Microscopic examination (if blood or protein is abnormal) 
 
○ Epithelial cells
 
○ Red Blood cells
 
○ WBC
 
○ Casts
 
○ Crystals
 
○ Culture (if positive: specify pathogen)
 
 
 
	

\* To assess the kidney function, use eGFR 2021 calculator (CKD-Epi creatinine equation). eGFR (based on CKD-Epi) will be measured at all time points when creatinine is measured.

\*\* Blood sampling for serum potassium and glucose on each dosing day (Day 1, 4, 7 and 10) and at the following time points: predose and 15 and 30 minutes, 1, 1.5, 2 and 4 hours post dose.

Descriptive statistics (n, mean, standard deviation (SD), median, minimum value (min), and maximum value (max)) will be presented for quantitative measurements of absolute value for continuous laboratory parameters (clinical chemistry and hematology) including serum potassium and glucose at baseline and each assessed visit as per SOA of protocol in on-treatment period for Safety analysis set. Counts and percentages will be produced for qualitative measurements measure laboratory parameters for on-treatment period for Safety analysis set.

As per protocol SOA Section 1.3, safety laboratory parameters data are not collected for follow up visit, therefore on-treatment period will be same as overall period.

Summary of liver monitoring/stopping event will be summarized by counts and percentages. Refer to protocol Appendix 5, Section 10.5 Liver safety for more description of liver events.

Participants listing of all clinical laboratory data will be produced for each treatment and period in Safety analysis set.

If a laboratory value which is expected to have a numeric value for summary purposes, has a non-detectable level reported in the database, where the numeric value is missing, but typically a character value starting with ‘<=’ or ‘=>’ (or indicated as less than x or greater than x in the comment field) is present, the number of significant digits in the observed values will be used to determine how much to add or subtract in order to impute the corresponding numeric value.

- Example 1: 2 significant digits = ‘<= x’ becomes  $x - 0.01$
- Example 2: 1 significant digit = ‘=> x’ becomes  $x + 0.1$
- Example 3: 0 significant digits = ‘<=x’ becomes  $x - 1$

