7. DISCONTINUATION OF STUDY INTERVENTION AND PARTICIPANT DISCONTINUATION/WITHDRAWAL

7.1. Discontinuation of study intervention

'Discontinuation' of study intervention refers to any participant who has not received all planned doses of the study intervention. In rare instances, it may be necessary for a participant to permanently discontinue study intervention. If study intervention is permanently discontinued, the participant should, if possible, continue other study procedures (e.g., safety), planned in the study protocol at the discretion of the investigator. If the participant does not agree to continue in-person visits, a modified follow-up must be arranged to ensure the collection of endpoints and safety information (e.g., telephone contact). See the SoA for data to be collected at the time of discontinuation of study intervention and follow-up and for any further evaluations that need to be completed.

[figure not shown]
The primary reason for premature discontinuation of the study intervention will be documented in the eCRF based on the list below:

Reasons	Additional items/Sub-reasons
AE	
Lost to follow-up	Participant Relocated Participant was Incarcerated Other Unknown
Participant Reached Protocol-Defined Stopping Criteria	Liver chemistry stopping criteria QTc Stopping criteria
Physician Decision	Specify
Pregnancy	
Protocol Deviation	Specify
Site Terminated by Sponsor	
Sponsor Terminated Study Treatment	
Study Terminated by Sponsor	
Withdrawal by Participant	Burden of Procedure Participant Relocated COVID-19 Pandemic Other
Other	Specify
Death	

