### Estimands for Safety

#### Cohort 1:

Test: Salbutamol HFA-152a MDI 200 μg

Reference: Salbutamol HFA-134a MDI 200 μg

The clinical question of interest for the safety secondary objective in Cohort 1 is -

What is the safety and tolerability profile of single doses 200 μg of salbutamol in Cohort 1 healthy participants delivered via MDIs?

The secondary safety estimand for Cohort 1 is described by the following attributes:

- The population is healthy male or female participants aged 18 to 55 years.
- The secondary safety endpoints are:
  - Incidence of AEs and SAEs
  - Absolute values for 12-lead ECGs recording of HR and QTc intervals at each assessed visit
  - Change from baseline for postdose 12-lead ECGs recording of HR and QTc intervals at each assessed visit
  - Absolute values of clinical laboratory parameters at each assessed visit
  - Absolute values of vital signs (systolic and diastolic blood pressure and pulse rate) at each assessed visit.
- Treatment condition is administration of salbutamol as a single 200 μg dose, given as 2 actuations each separated by a 20-second interval, each delivering 100 μg of salbutamol (as salbutamol sulfate) as the ex-valve dose for the HFA-152a MDI or HFA-134a MDI.
- The ICEs and estimand strategies are as follows:

- Study treatment discontinuation due to any reason (treatment policy strategy). Interest lies in the group of participants irrespective of whether they completed the study intervention.
- Occurrence of emesis or coughing on dosing (treatment policy strategy).
- Dosing error: Considered less than or more than prescribed dose (treatment policy strategy).
- Use of prohibited or rescue medication which impacts the PK parameters (Treatment policy strategy).
- The population level summaries to be estimated are:
  - Number and percentages for incidence of AEs and SAEs
  - Mean of absolute values for 12-lead ECGs recording of HR and QTc intervals at each assessed visit
  - Mean of change from baseline values for postdose 12-lead ECGs recording of HR and QTc intervals at each assessed visit
  - Mean of absolute of clinical laboratory parameters including vital signs (systolic and diastolic blood pressure and pulse rate) at each assessed visit

Cohort 2:

Test: Salbutamol HFA-152a MDI 800  $\mu$ g

Reference: Salbutamol HFA-134a MDI 800  $\mu$ g

The clinical question of interest for the safety secondary objective in Cohort 2 is -

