#### **4.5.3.2. Vital Signs**

The following vital signs measurements will be measured in a supine position after 5 minutes rest at baseline and each assessed visit.

- Systolic and Diastolic blood pressure
- Pulse rate

Descriptive statistics (n, mean, standard deviation (SD), median, minimum value (min), and maximum value (max)) will be presented at baseline, absolute value of vital signs parameters at each assessed visit for on-treatment period for Safety analysis set.

As per protocol SOA Section 1.3, safety vital signs data are not collected for follow up visit, therefore on-treatment period will be same as overall period.

Participants listing for all vital signs data will be produced for each treatment and period in Safety analysis set.

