#### 4.5.3.3. ECG

The arithmetic mean of the three recorded 12-lead ECGs measurements will be presented in all data summaries of 12-lead ECGs measurements at predose and single measurement of post dose for days 1, 4, 7 and 10 and discharge. ECG measurements will be recorded, including heart rate (HR), PR interval, QRS duration, QT interval, and RR interval. QT intervals will be based on Fridericia's formula and reported as per captured in eCRF:

Descriptive statistics (n, mean, standard deviation (SD), median, minimum value (min), and maximum value (max)) will be presented at baseline, and absolute and change from baseline for HR, QTc and other ECG parameters at each assessed visit for on-treatment period for Safety analysis set.

As per protocol SOA Section 1.3, safety ECG data are not collected for follow up visit, therefore on-treatment period will be same as overall period.

Participants listings will be provided for all 12 lead ECGs values and findings including abnormal ECGs for each treatment sequence and period in Safety analysis set.

[figure not shown]

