#### **6.2.2. Study Period**

Assessments and events will be classified within each cohort according to the time of occurrence relative to the study treatment period (days).

**Pre-Treatment:** For the presentation of serious adverse events (SAEs), concomitant medications, and other assessments in pre-treatment is defined as -

Date of assessment < Study treatment start date of period 1 (day 1).

**On-Treatment:** For the presentation of adverse events (AEs), serious adverse events (SAEs), concomitant medications, 12-lead ECG, vital signs, and other assessments in on-treatment is defined as -

Study treatment start date of period 1 (day 1) <= Date of assessment <= Study treatment stop date of period 4 (Day 10) or early withdrawal + 1 day

Worsening in AE (change in AE severity from lower severity to higher severity category) relative to the pre-study treatment state will also be considered as on-treatment AE.

If time of assessment or study treatment is not collected (missed), the following assessment on the first dose date will be assumed to be taken prior to the first dose and therefore considered pre-treatment.

As per study design, Four Treatment Periods of the study are defined below.

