#### **Treatment Period 4 (Day10):**

Treatment Period 4 dose start time <= Treatment Period 4 < Treatment Period 4 dose start time +1 day

**Post-Treatment:** For the presentation of adverse events (AEs), serious adverse events (SAEs), concomitant medications, 12-lead ECG, vital signs and laboratory assessments in post-treatment is defined as

Date of assessment > Study treatment stop date of period 4 (Day 10) or early withdrawal + 1 day.

Please refer Section [6.2.6](#) for handling of missing and partial dates of assessments.

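### Laboratory, vital sign and ECG tables stop at the on-treatment period, which is not the overall period for a participant who stops dosing but stays in the study

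*SAP*

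**What the plan says.** SAP 4.5.3.1 restricts its laboratory summaries to the on-treatment period and explains that "safety laboratory parameters data are not collected for follow up visit, therefore on-treatment period will be same as overall period". SAP 4.5.3.2 says "safety vital signs data are not collected for follow up visit, therefore on-treatment period will be same as overall period", and SAP 4.5.3.3 says "safety ECG data are not collected for follow up visit, therefore on-treatment period will be same as overall period".

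SAP 6.2.2 ends the on-treatment period at "Study treatment stop date of period 4 (Day 10) or early withdrawal + 1 day". It then sets up a post-treatment class for the same kinds of data ("12-lead ECG, vital signs and laboratory assessments in post-treatment is defined as"), with the rule "Date of assessment > Study treatment stop date of period 4 (Day 10) or early withdrawal + 1 day". It does not say whether *early withdrawal* means stopping treatment or leaving the study. For AEs, SAP 4.5.2 is specific: on-treatment runs to the study treatment stop date plus 1 day, and the main AE tables are produced for both the overall and the on-treatment periods.

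The safety estimand in SAP 4.3.1.1 lists "Study treatment discontinuation due to any reason (treatment policy strategy") among its intercurrent events, and its rationale says that laboratory, ECG and vital sign data matter whatever intercurrent events occur. Protocol 7.1 says that after permanent discontinuation of the intervention "the participant should, if possible, continue other study procedures (e.g., safety), planned in the study protocol", subject to the investigator's discretion.

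**The concern.** The SAP's reasoning considers only whether anything is collected at the follow-up visit. It does not consider a participant whose dosing ends before Day 10 but who is still being assessed in the clinic.

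The protocol provides for such people. Section 7.1 asks for continued safety procedures where possible. The QTc criteria in 7.1.2 withdraw a participant from the intervention, not from the study. Section 8.4.6 lets a participant who becomes pregnant continue other procedures.

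At stake is agreement between the safety tables and their estimand. A treatment-policy strategy means that values obtained after discontinuation count. If they are classed as post-treatment and only on-treatment values are tabulated, the tables follow a while-on-treatment rule for exactly the participants in whom the two strategies differ. Some of them may have stopped because of an AE or an ECG finding.

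**Working it through.** There is no stated figure to reproduce. The check compares the on-treatment window with the scheduled safety days.

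**Inputs**
- Dosing on Days 1, 4, 7 and 10; discharge on Day 11 (Protocol 4.1).
- Haematology, chemistry and urinalysis at screening, Day -1 and discharge only (Schedule of Activities, footnote f). The discharge panel is therefore the only scheduled post-dose panel.
- Vital signs and ECG on each dosing day and at discharge (footnotes h and i). Potassium and glucose on each dosing day (footnote g).
- End of on-treatment under reading A, treatment stop: day of last dose + 1.
- End of on-treatment under reading B, leaving the study, or the calendar limit of Day 10 + 1: Day 11 for someone who stays to discharge.

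**Result for a participant who stays to Day 11**

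| Last dose | Window end, A | Scheduled safety days outside, A | Window end, B | Outside, B |
|---|---|---|---|---|
| Day 1 | 1 + 1 = Day 2 | 4, 7, 10, 11 | Day 11 | none |
| Day 4 | 4 + 1 = Day 5 | 7, 10, 11 | Day 11 | none |
| Day 7 | 7 + 1 = Day 8 | 10, 11 | Day 11 | none |
| Day 10 | 10 + 1 = Day 11 | none | Day 11 | none |

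The last row is the completer, for whom the SAP's equality is right. In the other rows, reading A loses at least the Day 11 panel, vital signs and ECG. The dosing-day values are lost only if they are still measured without a dose. With a last dose on Day 4, the Day 11 panel falls 11 - 5 = 6 days beyond the window. A stopper who leaves with exit assessments within 1 day of the last dose loses nothing under either reading.

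**Which reading?** SAP 6.2.2 sets one on-treatment window for AEs, ECG, vital signs and other assessments together. SAP 4.5.2 gives the AE window as treatment stop + 1 day. The two sections agree on AEs only under reading A. The period windows in 6.2.2 also fit completers only: Periods 1 to 3 each close at the next dose, which a stopper may never receive.

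**The case against.** The strongest reply is that *early withdrawal* names the exit visit. Footnotes c and d of the Schedule of Activities use the term that way, paired with discharge. The window would then close one day after the visit at which the panel, vital signs and ECG are taken, and nothing scheduled would fall outside. The SAP also appears to intend no omission: it asserts equality, summarises each assessed visit, and names discharge among the ECG summaries. That reading is possible. But it leaves 6.2.2 at odds with 4.5.2 for AEs, and two programmers could reasonably build different tables.

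Other points stand and limit the concern:
- Staying in the study after stopping is only where possible and at the investigator's discretion.
- Values that prompt a stop on a dosing day are on-treatment under either reading. In the Day 4 example, the discharge panel comes 11 - 4 = 7 days after the last dose, and nothing shows that such late values are the abnormal ones.
- Follow-up is normally a telephone call. Values from a discretionary visit have no obvious row in a by-visit table.

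A reader might infer that the equality is false for everyone who stops early, or that the values survive only in listings. The documents support neither. Exit assessments within a day of the last dose stay in. Clinically significant laboratory, vital sign and ECG findings are recorded as AEs (Protocol 8.3.2 to 8.3.4), and the main AE tables cover the overall period. The liver-event summary in SAP 4.5.3.1 carries no on-treatment limit.

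**Conclusion.** The point holds in limited form. The stated equality is correct for completers and for stoppers assessed within 1 day of their last dose. It is not secured for a participant who stops dosing and stays. On the reading that reconciles SAP 6.2.2 with 4.5.2, that participant's later values leave the summary tables, including the only scheduled post-dose haematology, chemistry and urinalysis panel. This conflicts with the treatment-policy strategy. On the leaving-the-study reading nothing scheduled is lost, but the SAP does not say which reading applies.

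The number affected cannot be computed, because the documents give no expected rate of early stopping. A reader might take 2 of 30 per cohort from the allowance of 30 randomised for 28 in the PK set. That is not supported: the PK set requires only one full dose period and one non-missing PK assessment, so an early stopper can remain in it. The effect is probably small, it is confined to descriptive secondary safety tables, and the primary PK results are untouched. The change is still worth making because it costs almost nothing.

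**What to change.** In SAP 4.5.3.1, 4.5.3.2 and 4.5.3.3, delete the clause equating the on-treatment and overall periods. Summarise scheduled laboratory, vital sign and ECG data, including the discharge or early-discontinuation assessment, over the overall (on- and post-treatment) period, as SAP 4.5.2 does for AEs.

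In SAP 6.2.2, give one analysis definition of the end of on-treatment, consistent with 4.5.2: study treatment stop date + 1 day. Taken alone this would fix the shorter window, so it must go together with the overall-period summaries; once those are in place, no scheduled value drops out because of it.

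The cost is SAP wording and a change to the record-selection flag. No new data and no change to study conduct are needed.
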